10.3. Primary Analysis

10.3.1. Procedure Time

Hypothesis:

The non-awake method is faster than the awake method.

Metrics:

Skin-to-skin surgical time
Intraoperative programming time
Total fluoroscopy used (time and dose)

Statistical Tests:

Test for normality (such as Jarque-Bera)
Unpaired, two-sided Student's t-tests (normally distributed continuous data) or Mann-Whitney rank sums test (skewed continuous data)
Significance at $\alpha < 0.05$, with no adjustment for the multiple comparisons

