7.6.3. Pulse Generator Placement and Data Collection for Both Arms

The IPG is implanted by making a pocket incision at the desired location, and creating a subcutaneous pocket by blunt dissection. The pocket should be created so that the IPG is parallel to the skin surface. Subcutaneous tunnels are made from the lead incision site(s) to the IPG implantation site, using a tunneling tool. The leads/extension is tunneled to the IPG site. The lead/extension is connected to the IPG, the IPG is placed in the subcutaneous pocket, and all incisions are closed.

Additional guidance on system placement is located in the device manuals distributed with each device.

System implantation visit include recording the following information:

- Device information
- Collection of complications or changes in medication
- Total operating room time
- Skin-to-skin surgical time
- Intraoperative programming time
- Total fluoroscopy used (time and dose)
- Final lead position

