7.11. Outcome Measures

7.11.1. Characterization of Procedure Time

Procedure time will be characterized along the following metrics

- Total operating room time (from prep to recovery)
- Skin-to-skin surgery time (from first incision to last suture)
- Programming time (time while delivering test stimulation to address proper lead placement)
- Fluoroscopy time

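### Section 10.3.1 tests one claim of a faster procedure on four co-equal measures, names none as deciding, and leaves total operating room time out of the between-arm comparison

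*Combined protocol and SAP*

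**What the plan says.** Procedure time is a primary variable (Section 2.3), and the Protocol Summary makes its reduction an objective. Neither place says which time is meant.

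Section 7.11.1 supplies a definition: "Procedure time will be characterized along the following metrics". It lists total operating room time (preparation to recovery), skin-to-skin time (incision to closure), programming time (test stimulation for lead placement) and fluoroscopy time. Section 7.6.3 has "Total operating room time" recorded at implantation in both arms.

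Section 10.3.1 then states the hypothesis "The non-awake method is faster than the awake method" and lists skin-to-skin time, intraoperative programming time, and fluoroscopy time and dose. Each is tested two-sided at 0.05 "with no adjustment for the multiple comparisons". The list is not ranked.

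Total operating room time is absent from Section 10.3.1. Section 2.5 includes surgery information among the additional data, and Section 10.5 promises summary statistics for such data.

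**The concern.** There are two linked gaps in the analysis of a primary variable.

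First, one hypothesis is attached to four measures with no rule joining them. Suppose skin-to-skin time is unchanged but fluoroscopy time falls. The plan does not say whether the hypothesis is then supported. Programming and fluoroscopy times each describe only part of the operation, and a lower radiation dose says nothing direct about duration. The study is non-blinded, so a choice of metric made after the results are known would be hard to defend.

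Second, the only listed metric that reaches beyond incision to closure is the one left out of the comparison. The arms differ in anaesthesia (Sections 7.6.1 and 7.6.2), and Section 7.6 leaves preparation and anaesthesia to each centre's practice. Time before incision or after closure could differ between arms, and no planned comparison would show it. A shorter skin-to-skin time might then be reported as a shorter procedure overall.

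**Working it through.** **1. The plan's own figures.** Table 2 gives 60 minutes (non-awake) and 90 minutes (awake). The difference is 90 − 60 = 30 minutes, and 30/90 = 33%, which matches the reduction cited in the Introduction. Neither place says which metric this is. The total of 50 patients in Section 10.2 cannot be reproduced, because no SD, power or deciding endpoint is given. For procedure time alone, with 25 per arm and two-sided 0.05, 80% power requires SD = 30 × √(25/2) / (1.960 + 0.842) ≈ 37.9 minutes. Whether 25 per arm suits the deciding metric therefore depends on which metric it is and on its SD, which the documents do not give.

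**2. The two lists side by side.**

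| Measure | 7.11.1 (definition) | 10.3.1 (tested) | A duration? |
|---|---|---|---|
| Total operating room time | yes | no | yes |
| Skin-to-skin time | yes | yes | yes |
| Programming time | yes | yes | yes |
| Fluoroscopy time | yes | yes | yes |
| Fluoroscopy dose | no | yes | no |

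One duration drops out and one non-duration comes in. Neither change is explained.

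**3. What skin-to-skin time covers.** In the awake arm the patient is brought to conscious sedation after approximate lead positioning (Section 7.6.1), so that step falls inside the window. Any anaesthetic preparation before incision, or recovery after closure, falls outside it in both arms. The documents give neither the size nor the sign of an arm difference there.

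**4. Error rate under an assumed rule.** Assume that any one significant result favouring non-awake would count as faster. Each two-sided 0.05 test rejects in that direction with probability 0.025 when there is no true difference.

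- One named metric: 2.5%.
- Four independent tests: 1 − 0.975⁴ = 1 − 0.9037 = 9.6%. This is the upper bound for jointly normal statistics with non-negative correlation.
- Three durations only, dose excluded, independent: 1 − 0.975³ = 7.3%.
- Four equicorrelated normal statistics, P(max > 1.96): 8.7% at correlation 0.3, 7.8% at 0.5, 6.5% at 0.7 and 4.7% at 0.9.
- Mixed correlations (skin-to-skin with programming 0.5, fluoroscopy time with dose 0.9, other pairs 0.3): 7.5%.

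Under the opposite rule, that all four must be significant, the rate is at most 2.5%. All correlations are assumptions. The figures also ignore site effects, although arm is fixed by site.

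**The case against.** The plan is open that it does not adjust, and a post-market study may choose that. This stands, but it settles the level of each test and not which test answers the hypothesis.

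It can be argued that skin-to-skin time is primary because it comes first in Section 10.3.1. The plan does not say so, and Section 7.11.1 puts total operating room time first.

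A plan need not test every time it records. Skin-to-skin time is a defensible measure of an operation, and total operating room time may partly reflect site logistics because each site uses one method (Section 6). This also stands. It is why total operating room time is proposed as an estimate and not as the deciding test. Nor is that time ignored: on a natural reading, Sections 2.5 and 10.5 would have it summarised. A summary is not a planned between-arm difference with an interval, so the gap is narrowed and not closed.

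Finally, a claim of speed resting on dose alone is implausible, and the plan contains no any-one-metric rule. That is correct. The 9.6% illustrates what an unstated rule would allow. Dropping dose lowers the bound to 7.3% and does not remove the ambiguity.

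**Conclusion.** The point holds in a limited form. The four tests are usable, but the plan does not define what result would establish the primary time hypothesis. It also plans no between-arm comparison of the one recorded time that extends beyond incision to closure.

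The rise from 2.5% to at most about 9.6% is conditional on an any-one-metric rule, on approximately normal and non-negatively correlated statistics, and on no site effect.

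Three stronger inferences are not supported:

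- A reader might infer that the plan's false-positive rate for this hypothesis is 9.6%, or 18.5% (1 − 0.95⁴) counting both directions. The plan states no rule from which either follows, and a result favouring awake placement would not support the hypothesis.
- A reader might infer that leaving out total operating room time flatters the non-awake arm. The documents say nothing about the direction of any difference outside skin-to-skin time.
- A reader might infer that skin-to-skin time is the wrong metric, or that the unlabelled times in Table 2 invalidate the sample size by themselves. Neither can be shown. The Table 2 question matters here because the deciding metric should be the one that was planned for.

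**What to change.** Amend Section 10.3.1 before between-arm results are examined:

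1. Establish which metric the 60 and 90 minutes in Table 2 describe. Then name one duration as deciding. Skin-to-skin time is a reasonable candidate if it is consistent with Table 2.
2. Report the between-arm difference in total operating room time with a 95% confidence interval, as a companion that does not decide the hypothesis, with the caveat that arm is fixed by site.
3. Treat programming time and fluoroscopy time and dose as supportive.
4. Word the conclusion by the metric tested, for example as a shorter skin-to-skin time.

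No patients, visits or data items are added. It is still a protocol amendment, and Section 12 requires approval by the appropriate regulatory agencies and the IRB before it takes effect. Because the study is non-blinded and Section 9.3 has an updated database sent at least quarterly, the amendment should record whether any between-arm times have already been seen.

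The result may be less favourable to non-awake placement, and the companion estimate will partly reflect site logistics. It may also be imprecise. With 25 per arm the half-width is 2.0106 × √(2/25) × SD = 0.57 SD, or about 11, 17 or 23 minutes at assumed SDs of 20, 30 or 40 minutes, before any allowance for site effects.

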3.1. Design

This is a post-market, prospective, multicenter, parallel designed, non-randomized, non-blinded, 6-month study. A minimum of 50 patients will be implanted from up to 4 active sites, coordinated by a single lead investigator.

Patients who have had a successful SCS trial and are indicated for permanent implantation will be approached to participate in this study prior to permanent implantation. Patients will be recruited and enrolled by physicians at any one of the involved sites. Each Investigator will only use one method (awake or non-awake) according to his/her typical practice. Patients will receive treatment from their enrolling physician.

[figure not shown]

Table 1: Study Schedule

Timing of visit	Activities at visit	Case Report Forms
Screening and Informed Consent (may be immediately after Trial System Explant)	Patient evaluated for eligibility Patient signs informed consent Schedule patient for baseline evaluation at treatment site	Enrollment Form Inclusion/Exclusion Criteria Form
Baseline Evaluation 7-28 days after screening	Patient completes questionnaires Complete history and physical exam Record current medication use Collect patient reported data	Baseline Self Evaluation Form Pain Location Form Pain Evaluation Form SF-MPQ-2 (Pain Quality) EQ-5D (Quality of life) Medication Form
Permanent System Implantation	Permanent system implantation Record any complications Record any changes in medication Discourage activation at discharge Save digital recording or EMG recording if system permits.	Surgery Form Adverse Event Form Programming Form (if programmed at discharge) Medication Form
Initial Programming Visit	Record any complications Record any changes in medication Provide patient with the patient programmer and charging system Record patient's global impression of satisfaction with the implant procedure.	Programming Form Paresthesia Coverage Form Patient Global Impression Form Medication Form
6 weeks 42 ± 7 days after activation	Record any complications Record any changes in medication Patient completes questionnaires Modify programming parameters (if necessary) Collect patient reported data	Follow-up Visit Form Pain Evaluation Form Pain Location Form Programming Form SF-MPQ-2 (Pain Quality) EQ-5D (Quality of life) Paresthesia Coverage Form Medication Form

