5.2. Exclusion Criteria

A patient will be excluded from participation in this study if they meet any one of the following criteria:

1. Patient currently participating in a clinical investigation that includes an active treatment arm.
2. Patient has an infusion pump or any implantable neurostimulation device
3. Patient has an existing medical condition that is likely to require repetitive MRI evaluation in the future (i.e. epilepsy, stroke, multiple sclerosis, acoustic neuroma, tumor)
4. Patient has an existing medical condition that is likely to require the use of diathermy in the future
5. Patient is immunocompromised
6. Patient has documented history of allergic response to titanium or silicone
7. Patient has a documented history of substance abuse (narcotics, alcohol, etc.) or substance dependency in the 6 months prior to baseline data collection
8. Female candidates of child bearing potential that are pregnant (confirmed by positive pregnancy test)

6. Patient Assignment to Procedure

Each patient who is willing to participate in the study, signs the informed consent, and complies with the inclusion/exclusion criteria will be enrolled in the study. Patients are considered enrolled in the study from the moment the patient has provided written informed consent. Each patient is enrolled chronologically on a patient enrollment log and given a patient number for the duration of the study.

Patients will be enrolled in a 1:1 fashion to the method of surgical implantation, either awake or non-awake. Patients will be treated by the enrolling physician. Patients recruited and enrolled at St. Luke's Neurological Associates or Thomas Jefferson University will undergo implantation under general anesthesia with EMG neuromonitoring for testing of the distribution of induced paresthesia ("non-awake"). Patients recruited and enrolled at Geisinger or Milton S. Hershey Medical Centers will undergo implantation of the device in an awake operation with local anesthetic and patient interaction for testing of the distribution of the induced paresthesia ("awake"). Each treatment arm will enroll a maximum of 30 patients. No blinding is necessary for the purposes of assigned study arm.

7. Methods and Procedures

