10.2. Sample Size Justification

Recent, retrospective studies of single center experience with the two procedures suggests the following complication and repositioning rates and procedure time (Falowski et al., 2011; Shils & Arle, 2012);;

Table 2: Outcome rates for sample size calculation

	Non-awake	Awake
Revisions for device failure	15%	30%
Lead repositioning for efficacy	1%	15%
Infection rate	4.5%	6.0%
Procedure time	60 minutes	90 minutes

Simulations based on these results indicated that the sample size required to reject the null hypothesis at the 5% significance level is a minimum of 50 patients, who will be enrolled 1:1 between the two procedures. Note that because neither procedure is currently considered the “gold standard”, and given the primary research objective of assessing safety and efficacy, it was determined that the sample size calculation should not be based on a formal hypothesis of non-inferiority with a pre-determined non-inferiority margin.

Sample Size Adjustments - Patients have already been approved for a permanent system implant, thus a screen failure rate of 0% is assumed. The objective of the study is to study the implant procedures, eliminating the need to account for non-responders to treatment.

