10.4. Secondary Analysis

10.4.1. Paresthesia coverage

Hypothesis:

The non-awake is comparable to the awake method in the proportion of the painful regions covered by paresthesia

Metrics:

Paresthesia overlap percentage

Extraneous paresthesia percentage

The regions marked on the Pain Location Form and Paresthesia Coverage form will be categorized as overlapping, uncovered pain, excess paresthesia, or none (see Table 3; Alo, Yland, Redko, Feler, & Naumann, 1999).

$$paresthesia\ overlap\ percentage = \frac{N_O}{N_U+N_O} \cdot 100$$

$$extraneous\ paresthesia\ percentage = \frac{N_E}{N_O+N_E} \cdot 100$$

Statistical Tests:

Test for normality (such as Jarque-Bera)

Unpaired, two-sided Student’s t-tests (normally distributed continuous data) or Mann-Whitney rank sums test (skewed continuous data)

Significance at $\alpha < 0.05$, with no adjustment for the multiple comparisons

		Paresthesia Coverage Form	
		Marked	Unmarked
Pain Location Form	Marked	Overlap N_O	Uncovered N_U
	Blank	Excess N_E	None N_N

Table 3: Pain-Paresthesia Comparison Categories

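### Procedure time and coverage: Student's equal-variance t-test holds 5% at the planned 1:1 split but drifts if arm sizes and SDs both differ; Welch's test would be a near-free safeguard (minor).

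*Combined protocol and SAP*

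**What the plan says.** Section 10.3.1 of the combined protocol and SAP begins with a "Test for normality (such as Jarque-Bera"). The result selects between "Unpaired, two-sided" Student's "t-tests (normally distributed continuous data) or Mann-Whitney rank sums test (skewed continuous data"). Section 10.4.1 repeats the rule for the two coverage percentages, including the "Mann-Whitney rank sums test (skewed continuous data") route. Neither section names an unequal-variance version of the t-test or looks at spread.

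On arm sizes, Section 10.2 asks for "a minimum of 50 patients, who will be enrolled 1:1 between the two procedures", and Section 6 also states 1:1. Section 3.1 says "A minimum of 50 patients will be implanted from up to 4 active sites". Section 6 ties each site to one technique and adds: "Each treatment arm will enroll a maximum of 30 patients". Section 10.6 limits the analysis to patients who complete the 6-week visit and excludes those with missing baseline values. Section 11 says that discontinued patients may not be replaced.

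Table 2 gives expected procedure times of 60 and 90 minutes. No SD is given for any endpoint or arm.

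**The concern.** Student's t-test pools the two variances. With equal arms, pooling gives the right standard error for the difference even when the variances differ. With unequal arms it does not. If the smaller arm is the more variable one, the standard error is too small and the test rejects too often. If the larger arm is more variable, the test rejects too seldom. The 95% interval that goes with the test has the same fault. A normality test examines shape, not spread, so it gives no warning.

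Nothing in the documents shows how 1:1 would be held. Each arm fills at the pace of its own sites, and exclusions from the analysis set could widen any gap. Procedure time is a primary variable and coverage is the secondary one, so the nominal 5% level of both comparisons is at stake. The direction of any error cannot be known beforehand.

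**Working it through.** **Inputs from the documents.** Two-sided test at 0.05 (10.3.1, 10.4.1); minimum total 50, planned 1:1, so 25:25 (10.2); at most 30 per arm (Section 6), so the most unequal enrolled split at a total of 50 is 30:20.

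**Input assumed.** The SD ratio between arms, taken as 1.5 or 2. The documents give no SD. If SD were proportional to the mean (also an assumption), Table 2 would give 90/60 = 1.5.

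**The plan's own figure.** The minimum of 50 comes from simulations said to "reject the null hypothesis at the 5% significance level". It cannot be reproduced, because the SD, the power and the endpoint that drives the number are not stated. The check below does not depend on it.

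**Large-sample check.** Let V be the variance that Student's test assigns to the difference in means, and T its true variance:

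- V = [((n1−1)s1² + (n2−1)s2²)/(n1+n2−2)] × (1/n1 + 1/n2)
- T = s1²/n1 + s2²/n2
- actual error ≈ 2 × [1 − Φ(1.96 × √(V/T))]

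*25:25, SDs 1 and 2.* V = [(24 + 24×4)/48] × (2/25) = 2.5 × 0.08 = 0.200. T = 1/25 + 4/25 = 0.200. V/T = 1, so the error is 5.0%.

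*30:20, smaller arm with twice the SD.* V = [(29 + 19×4)/48] × (1/30 + 1/20) = 2.1875 × 0.08333 = 0.1823. T = 1/30 + 4/20 = 0.2333. V/T = 0.781; 1.96 × √0.781 = 1.732; error ≈ 8.3%.

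*30:20, larger arm with twice the SD.* V = [(29×4 + 19)/48] × 0.08333 = 2.8125 × 0.08333 = 0.2344. T = 4/30 + 1/20 = 0.1833. V/T = 1.278; 1.96 × √1.278 = 2.216; error ≈ 2.7%.

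**Simulation.** Normal data, equal means, at least 100,000 trials per setting; repeat runs differ by a few tenths of a point or less.

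| Split | SD ratio | Student, larger arm more variable | Student, smaller arm more variable | Welch |
|---|---|---|---|---|
| 25:25 | 1.5 or 2 | about 5% (arms equal) | about 5% (arms equal) | about 5% |
| 28:22 | 1.5 | about 4.0% | about 6.2% | about 5% |
| 28:22 | 2 | about 3.7% | about 7.0% | about 5% |
| 30:20 | 1.5 | about 3.5% | about 7% | about 5% |
| 30:20 | 2 | about 3% | about 8.5% | about 5% |

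**The rule as written.** With the Jarque-Bera step followed by Student or Mann-Whitney, at 30:20 and ratio 2, the error is 3.0% or 8.5%. The normality step does not change the picture. With Welch in the t-test branch it is 5.0% or 5.4%.

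**Cost in power when the SDs are equal** (standardised difference 0.8). At 30:20, Student 77.6% and Welch 77.2%, a loss of 0.4 points. At 25:25, 79.1% and 79.1%, a loss under 0.1 point.

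**Limits of Welch.** For lognormal data with equal means and log-scale SDs of 0.3/0.6, 0.4/0.8 and 0.5/1.0 (assumed), with the larger spread in the 20-patient arm, Welch's error at 30:20 is about 7%, 8% and 10%. Mann-Whitney is also affected by unequal spread: for normal data at 30:20 and ratio 2 its error is 4.1% or 7.3%.

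**The case against.** The strongest reply is that the plan states 1:1 twice, and that at 1:1 there is nothing to correct. That stands. A reader might infer that the plan's true error rate is 3% to 8.5%. The documents do not support this: that range needs both the most unequal split the cap allows and an SD ratio of 2 that appears nowhere in them. At 26:24 with ratio 2, Student's error is 4.7% or 6.0%, so a small departure from the plan moves the error by about a point or less.

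Assignment by site does not by itself imply unequal variances. Different surgeons and techniques make them possible, but no figure in the documents shows them.

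A reader might also infer that Welch removes the problem at no cost and should replace the whole two-step rule. That goes too far. There is a small power cost, and Welch does not hold 5% for skewed data with unequal spread, which is where the plan turns to Mann-Whitney. At 25:25 the normality step adds little error (5.3% to 5.7% for lognormal times), so dropping it is a trade-off rather than a correction.

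Finally, confounding and clustering by site are the larger threats. With two sites per arm, 25 patients per arm and an assumed intraclass correlation of 0.05, the error is about 12% with either t-test. That is a separate matter. It limits what this change can achieve but is no reason to keep the equal-variance assumption.

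**Conclusion.** The point holds in conditional form and is minor. Sections 10.3.1 and 10.4.1 rely on an equal-variance test and describe nothing that secures the equal arms which would make it safe. If enrolment follows the plan, the error stays near 5%. If the arms drift apart and the SDs differ, it moves in either direction, by one to two points at 28:22 and by up to about 3.5 points at 30:20. These sizes rest on normal data and assumed SD ratios of 1.5 to 2. They do not show that the plan's error rate is wrong, only that it depends on conditions the plan does not control.

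**What to change.** In the t-test branch of Sections 10.3.1 and 10.4.1, replace Student's test with Welch's unequal-variance t-test. Report the mean difference (minutes for times, percentage points for coverage, the metric's own unit otherwise) with its 95% confidence interval. Leave the Mann-Whitney route for skewed data as it is.

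The change is to wording only. When variances are equal it costs at most about 0.4 points of power at 30:20 and under 0.1 point at 25:25. The text should not present it as a remedy for skewed data with unequal spread or for site effects, which need their own treatment.
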